# Table 6.aTAK-020 DLTs

aPTT=activated partial thromboplastin time, eGFR= estimated glomerular filtration rate.

# 6.2 Justification for Study Design, Dose, and Endpoints

## **Study Design**

# Parts 1 and 2

This study will be performed in healthy subjects rather than the target subject population (ie, diseased patients) in order to collect safety and tolerability information that will not be biased by common comorbidities. The study is double-blind in order to avoid subjective bias in the assessment of safety, tolerability, and pharmacological effects of the study medication. Placebo will be administered as a control in order to establish the frequency or magnitude of changes in clinical endpoints that may occur in the absence of active treatment. Sentinel dosing is intended to be used in the first cohort in Part 1, but it may also be used in other cohorts if exposure is observed in fewer than 3 subjects or by agreement with Takeda and the investigator.

# **Dose and Dose Regimen**

The starting dose of 0.1 mg was based on both the Food and Drug Administration (FDA) guidance [7] and PK/PD modeling which predicted 20% BTK occupancy, which is considered to represent a minimum anticipated biological effect level.

Currently doses of 0.1, 0.5, 2.5, 4.4, 8.8, 17.5, 35, 70, and 105 mg have been tested in the SRD and 3.75, 5.75, 13 and 25 mg in the MRD and were shown to be safe and well tolerated. Draft PK data are summarized in Table 6.b and Table 6.c for the SRD and MRD, respectively.

Cohort (Dose)	C max (ng/mL)	T max * (hr)	AUC 24 (ng*h/mL)	AUC t (ng*h/mL)	$AUC_{\infty}$ (ng*h/mL)	Half-life (hr)

## Table 6.b Summary of TAK-020 PK Parameters Cohorts 1 to 9 in SRD

\*Median value.

# Table 6.c Summary of TAK-020 PK Parameters Cohorts 1 to 7 in MRD

Cohort (Dose)	C max (ng/mL)	T max * (hr)	AUC 24 (ng*h/mL)	AUC t (ng*h/mL)	AUC∞ (ng*h/mL)	Half-life (hr)	Accumulation Index

\*Median value.

Accumulation index=D9AUC24/D1AUC $\infty$ · TBD=to be determined.

Furthermore, plasma protein binding of TAK-020 in humans is higher than in the rat, (98.9% and 98.0% respectively) resulting in lower exposures to unbound (free) TAK-020 in humans at a given total exposure. Therefore unbound exposure estimates have been used to refine the dose escalation.

ТАК-020	
Study No. TAK-020-1001	Page 31 of 101
Protocol Incorporating Amendment No. 4.0	27 March 2017

The exposure at the maximum proposed dose would not exceed 1808 ng\*h/mL (total) and 19.9 ng\*h/mL (unbound) which is 2.19-fold unbound exposure at the LOAEL, and corresponds to a safety factor of 0.43.

As the PK  $t_{1/2z}$  for this compound remains short, PK washout would be expected within 24-hours and time dependency of PK could be evaluated without the need for any additional washout period following Day 1 in the MRD study Part 2. Further, due to the short  $t_{1/2z}$ , no accumulation in plasma PK is expected during the MRD. PD washout following Day 1 in MRD was not considered necessary for evaluation.

The following safety variables will be used to describe the safety and tolerability of TAK-020:

- Physical examination findings.
- TEAEs.
- Clinical laboratory test results.
- Vital sign measurements and weight.
- 12-lead ECGs.

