A comprehensive series of nonclinical safety studies (Good Laboratory Practice [GLP]) was conducted with TAK-020 to support early human studies. No safety concerns were identified in safety pharmacology assessments (human ether-à-go-go-related gene [hERG], electrocardiography, cardiovascular, respiratory, central nervous system [CNS]), genetic toxicology studies (Ames, in vitro micronucleus, in vivo micronucleus), or an in vivo phototoxicity study. In addition, daily repeated-dose toxicology studies of 28 days in duration have been conducted in rats and dogs. The oral dose levels were 5, 25, and 75 mg/kg in the rat study and 5, 20, and 75 mg/kg in the dog study. The no-observed–adverse-effect level (NOAEL) in the rat study was 5 mg/kg (AUC=63 ng\*h/mL, sexes combined). The NOAEL in the dog study was 20 mg/kg (AUC=518 ng\*h/mL, sexes combined). At the low-observed-adverse-effect-level (LOAEL) the combined sex AUC in rat and dog were 431 ng\*h/mL and 6418 ng\*h/mL, respectively.

For further information on TAK-020, please refer to the Investigator's Brochure for TAK-020.

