## 6.1.1 Dose Escalation

The dose escalation scheme is shown in Figure 6.b. All decisions concerning dose escalation will be made by Takeda (at a minimum, the clinical science representative(s) and pharmacovigilance physician) and the principal investigator (PI). Additionally, Takeda and the PI may jointly decide to not escalate the dose for a particular cohort, but rather administer the same or a lower dose level to the next cohort.

The AUC24 will be calculated for each subject and subsequently the geometric mean of AUC24 will be determined for each cohort (excluding placebo). Dose escalation will proceed to a dose level that is predicted to give a TAK-020 unbound AUC of (19.8 ng\*h/mL) approximately 2-fold higher than the unbound AUC of the rat LOAEL.

There will be a minimum period of 5 days between each dose escalation to allow for review of safety, tolerability and PK data. The blind of the PK data will remain intact during these reviews by using an alias number as the subject identifier instead of randomization sequence number for each subject.

For each dose level administered/completed cohort, the PI and Takeda will carefully review the available blinded safety, tolerability and blinded PK data (if data is available in time for the planned review). They will determine whether dosing should stop or continue (and, if continue, at what dose, including whether to repeat the previous dose), whether additional sequential dosing

TAK-020	
Study No. TAK-020-1001	Page 27 of 101
Protocol Incorporating Amendment No. 4.0	27 March 2017

should be implemented in future cohorts or whether the blind should be broken to identify whether the subjects received TAK-020 or placebo. In the next cohort (Part 1), exposures may be increased by a maximum of 5-fold as long as the predicted exposure will be below that at the NOAEL in the most sensitive nonclinical species, which is the rat (63 ng·hr/mL, sexes combined). For doses with exposure above the NOAEL doses may be increased to give a maximum of 2-fold increase in exposure. Doses may also be decreased as appropriate. In cohorts in the next part of the study (Part 2), the doses may be increased as long as the maximum exposure multiplier is below 2-fold. The predicted steady state exposure in the MRD will not exceed the maximum exposure observed in the SRD.

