## **TAK-020 nonclinical studies**

Nonclinical toxicology studies were conducted with TAK-020 in rats and dogs. The rat was identified as the most sensitive toxicology species. Target organ toxicity in a GLP 4-week rat toxicology study administered doses in excess of the NOAEL (AUC>63 ng·hr/mL, sexes combined) was seen in the liver and kidney. Liver toxicity was seen in rats at an AUC of greater or equal to 431 ng·hr/mL (sexes combined), and kidney toxicity seen at an AUC of 2030 ng·hr/mL. Reversibility was not tested in the 4-week GLP rat study, however in a 2-week rat study, liver changes were fully reversible after a 2-week recovery period. In the absence of nonclinical information on reversibility, the kidney changes will be considered not reversible. Markers of kidney injury will be monitored in this study.

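### Do the 2.19-fold LOAEL multiple and the 0.43 safety factor in Protocol 6.2, which are not reciprocals, call for a change to the plan?

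*Protocol*

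**What the plan says.** Section 6.2 of the protocol justifies the top of the dose range by comparing human exposure with exposure at the rat LOAEL. It first explains why unbound drug is compared: "plasma protein binding of TAK-020 in humans is higher than in the rat, (98.9% and 98.0% respectively"). It adds: "Therefore unbound exposure estimates have been used to refine the dose escalation".

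It then gives the ceiling. "The exposure at the maximum proposed dose would not exceed 1808" ng*h/mL in total and 19.9 ng*h/mL unbound, "which is 2.19-fold unbound exposure at the LOAEL, and corresponds to a safety factor of 0.43".

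The rat figure behind the comparison is given elsewhere. Section 4.1 says that at the LOAEL "the combined sex AUC in rat and dog were 431" ng*h/mL for the rat (the dog figure follows). The nonclinical part of Section 6.2 repeats the value: "Liver toxicity was seen in rats at an AUC of greater or equal to 431" ng*h/mL.

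Section 6.1.1 states the escalation goal on the same scale: "Dose escalation will proceed to a dose level that is predicted to give a TAK-020 unbound AUC of" 19.8 ng*h/mL, which it describes as roughly twice the unbound exposure at the rat LOAEL. The unbound LOAEL exposure is not printed, and the term safety factor is not defined.

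**The concern.** The sentence in Section 6.2 presents the multiple and the safety factor as two forms of one comparison. If the human exposure is a given multiple of the LOAEL exposure, the safety factor should be one over that multiple. A multiple of 2.19 goes with 0.46, and a factor of 0.43 goes with 2.33. At least one printed figure must therefore be off, or the two rest on different inputs.

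The subject makes this worth checking. Healthy volunteers are to be taken above the exposure at which liver toxicity appeared in rats, and this sentence is where the protocol quantifies by how much. Had the wrong member of the pair been feeding an exposure limit, the limit itself would be in doubt. On the printed inputs the misfit also runs in the reassuring direction, because 2.19 makes the excess over the LOAEL look slightly smaller than 2.31 does.

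**Working it through.** **Inputs, all printed in the protocol**

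| Quantity | Value | Place |
|---|---|---|
| Maximum total human AUC | 1808 ng*h/mL | Section 6.2 |
| Maximum unbound human AUC | 19.9 ng*h/mL | Section 6.2 |
| Human binding 98.9%, so unbound fraction | 0.011 | Section 6.2 |
| Rat binding 98.0%, so unbound fraction | 0.020 | Section 6.2 |
| Rat LOAEL total AUC | 431 ng*h/mL | Sections 4.1 and 6.2 |

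**Step 1. Reproduce the protocol's figures.** Unbound AUC = total AUC x unbound fraction.

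- Human: 1808 x 0.011 = 19.89, which matches 19.9.
- Rat LOAEL: 431 x 0.020 = 8.62.
- Safety factor = rat LOAEL unbound / human unbound = 8.62/19.9 = 0.433, which matches 0.43.
- Multiple = human unbound / rat LOAEL unbound = 19.9/8.62 = 2.31, which does not match 2.19.

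Relative to 2.31, the printed multiple is low by 1 - 2.19/2.309 = 5.1%.

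**Step 2. Test whether rounding of the pair explains it.**

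- A factor printed as 0.43 lies between 0.425 and 0.435, so the multiple lies between 1/0.435 = 2.30 and 1/0.425 = 2.35.
- A multiple printed as 2.19 lies between 2.185 and 2.195, so the factor lies between 1/2.195 = 0.456 and 1/2.185 = 0.458.
- Implied unbound LOAEL AUC from 0.43: 19.85 x 0.425 = 8.44 to 19.95 x 0.435 = 8.68.
- Implied unbound LOAEL AUC from 2.19: 19.85/2.195 = 9.04 to 19.95/2.185 = 9.13.

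The ranges do not overlap, so the pair is inconsistent whatever inputs were used.

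**Step 3. Test whether rounding of the inputs could yield 2.19.**

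- Holding 19.9 as printed and moving 19.9, 431 and 98.0% to their rounding limits: 19.85/(431.5 x 0.0205) = 2.24 to 19.95/(430.5 x 0.0195) = 2.38. This excludes 2.19.
- Starting from the total AUC and also letting human binding move within its rounding: (1807.5 x 0.0105)/(431.5 x 0.0205) = 2.15 to (1808.5 x 0.0115)/(430.5 x 0.0195) = 2.48. This includes 2.19.
- Example: unbound fractions of 1.06% and 2.03% would print as 98.9% and 98.0% binding, and give (1808 x 0.0106)/(431 x 0.0203) = 19.16/8.75 = 2.19.

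So 2.19 could come from unrounded fractions, with 19.9 and 0.43 computed from the rounded ones. The documents do not say so.

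**Step 4. Look for anything that uses the multiple.**

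- Part 1 escalation (Section 6.1.1): steps of at most 5-fold in exposure while below the rat NOAEL of 63 ng*h/mL, and at most 2-fold above it. The multiple is not used.
- Escalation goal (Section 6.1.1): an absolute unbound AUC of 19.8, glossed as about twofold. On the printed inputs 19.8/8.62 = 2.30. Both 2.19 and 2.31 fit the gloss.
- Ceiling (Section 6.2): absolute values, 1808 total and 19.9 unbound. The multiple describes the ceiling and does not define it.
- Part 2 (Sections 6.1 and 6.1.1): 2-fold steps and a cap at the highest exposure observed in Part 1. The multiple is not used.
- Stopping criteria and dose-limiting toxicities (Section 6.1.2, Table 6.a): clinical events, laboratory values and QTcF. The multiple is not used.
- SAP: no analysis refers to the LOAEL.

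**The case for a change.** The case for acting is respectable. The contradiction can be shown from one sentence and does not depend on guessing the sponsor's inputs. Three printed numbers (1808, 19.9 and 0.43) agree with the printed binding and LOAEL values, and 2.19 stands alone. Other comparators do not rescue it: total AUC gives 1808/431 = 4.19, and the unbound rat NOAEL gives 19.9/(63 x 0.020) = 15.8. The sentence concerns the margin for healthy volunteers, the error on the printed inputs is in the reassuring direction, and Figure 6.b still lists Part 2 Cohorts 5 to 7 as undetermined. Correcting it would take one sentence.

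What stands is the inconsistency itself. What does not stand is calling it a misstated safety margin. The number the protocol labels the safety factor is 0.43; it reproduces, and it is the less favourable of the two. A reader who takes either figure learns that the maximum exposure is more than twice the rat LOAEL exposure. The unbound LOAEL value is not hidden either, since it follows in one multiplication from Sections 4.1 and 6.2. The remaining Part 2 doses are bounded by observed Part 1 exposure, whichever multiple is right.

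The 19.8 in Section 6.1.1 and the 19.9 in Section 6.2 do not add a second contradiction. One is a level that escalation is predicted to reach and the other a level not to be exceeded. They differ by 0.1/19.9 = 0.5%, and the first lies below the second.

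**Conclusion.** The two figures cannot both be right as forms of one ratio, and 2.19 is probably the one that does not fit: 2.31 on the printed inputs, a difference of about 5%. It is a clerical slip in a descriptive clause. The exposures that set the ceiling and the safety factor are printed alongside it and reproduce, and no decision rule or analysis takes the multiple as an input, so replacing it would alter nothing the trial does or concludes. No change to the plan is called for.

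This rests on three assumptions. First, safety factor means LOAEL exposure divided by human exposure; the protocol does not define it, but that reading reproduces 0.43. Second, the comparator is the rat LOAEL AUC of 431 ng*h/mL at 98.0% binding. Third, that 2.19 is the wrong member of the pair is an inference, because unrounded binding fractions could produce it (raw ratio 2.15 to 2.48). If they did, the 0.43 would be the figure to reconcile, and the conclusion about the plan would be the same. None of this bears on which exposure limit is appropriate, a matter for the sponsor and the investigator.

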## Part 2 MRD

Part 2	Cohort $1 \rightarrow$	Cohort $2 \rightarrow$	Cohort 3→	Cohort 4→	Cohort $5 \rightarrow$	Cohort 6→	Cohort 7
MRD	3.75 mg	5.75 mg	13 mg	25 mg	X mg TBD	X mg TBD	X mg TBD
Evaluation	TAK-020 or	TAK-020 or	TAK-020 or	TAK-020 or	TAK-020 or	TAK-020 or	TAK-020 or
	placebo	placebo	placebo	placebo	placebo	placebo	placebo

TBD=to be determined for actual dose level when PK data from the previous cohort is available.

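### Section 6.1.1 makes the PK review at each escalation conditional, while other sections require it and open Part 2 doses depend on it; separately, the 2.19-fold multiple in Section 6.2 should read 2.31-fold

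*Protocol*

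**What the plan says.** Section 6.1.1 (Dose Escalation) is the operative text. It reserves time for the review: "There will be a minimum period of 5 days between each dose escalation to allow for review of safety, tolerability and PK data". It then says that the investigator and sponsor look at blinded safety and tolerability data and "blinded PK data (if data is available in time for the planned review". The same section states, without condition and without tying it to the review date, that AUC24 is computed per subject and its geometric mean per cohort. For Part 2 it sets the step limit, "the doses may be increased as long as the maximum exposure multiplier is below 2-fold", and caps predicted steady-state exposure at the highest exposure observed in Part 1.

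Other places treat the PK review as required:

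- Section 11.0: the sponsor and investigator review PK for each cohort before any further cohort is dosed.
- Section 13.2: a blinded safety and PK review takes place after each cohort and before the next escalation. It cites Section 6.1.1 as the description of that review.
- Section 6.1, Part 2: each dose is chosen from Part 1 data and from the preceding Part 2 cohort.
- Figure 6.b, Part 2 table, on the open doses: "TBD=to be determined for actual dose level when PK data from the previous cohort is available".
- Sections 2.0 and 6.1: at least 24 hours of PK from the previous cohort must be reviewed, but this is written for Part 1 only.

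On the exposure multiple, Section 6.2 limits exposure to 1808 ng*h/mL total and 19.9 ng*h/mL unbound, "which is 2.19-fold unbound exposure at the LOAEL, and corresponds to a safety factor of 0.43". It also states that "plasma protein binding of TAK-020 in humans is higher than in the rat, (98.9% and 98.0% respectively"). Section 4.1 says that at the LOAEL "the combined sex AUC in rat and dog were 431" ng*h/mL for the rat (6418 for the dog). Section 6.2 repeats the rat figure: "Liver toxicity was seen in rats at an AUC of greater or equal to 431" ng*h/mL.

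**The concern.** A team that follows Section 6.1.1 could hold the review on schedule without PK and believe that it had complied. Section 13.2 does not correct this, because it points back to Section 6.1.1.

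The Part 2 limits are exposure limits, and dose is an imperfect stand-in for exposure. Single-dose data may also not carry over fully to steady state. Section 4.1 lists CYP3A4, CYP2C19 and CYP1A2 as the main metabolic routes, and reports weak induction of CYP1A2 and CYP3A4 and inhibition of CYP2C19. Section 13.1.3.2 plans a Day 9 against Day 1 comparison to look for time dependency. Observed multiple-dose PK is what confirms the prediction on which the next dose rests.

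The multiple in Section 6.2 tells a reader how far above the rat liver-toxicity exposure healthy volunteers may go. Its two expressions in one sentence disagree.

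**Working it through.** **PK review: which cohorts it affects**

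- Part 1: Sections 6.2 and 8.1.3 report all nine doses, 0.1 to 105 mg, as tested. The conditional wording no longer matters there.
- Part 2: Section 6.2 reports 3.75, 5.75, 13 and 25 mg as tested. Figure 6.b leaves Cohorts 5 to 7 to be determined, and seven is a maximum.
- Still open: at most 7 - 4 = 3 cohorts, so at most 3 x 8 = 24 randomized and 3 x 6 = 18 on TAK-020.
- Dose steps so far: 5.75/3.75 = 1.53; 13/5.75 = 2.26; 25/13 = 1.92. The second exceeds 2-fold in dose while the cap is 2-fold in exposure, so the dose ratio alone does not settle compliance.

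**Exposure multiple**

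Inputs: total AUC 1808 and unbound AUC 19.9 (Section 6.2); binding 98.9% human and 98.0% rat (Section 6.2); rat LOAEL AUC 431 (Sections 4.1 and 6.2). Unbound AUC = total AUC x (1 - binding).

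1. Human unbound: 1808 x 0.011 = 19.89. This reproduces the stated 19.9.
2. Rat LOAEL unbound: 431 x 0.020 = 8.62.
3. Safety factor: 8.62/19.9 = 0.433. This reproduces the stated 0.43.
4. Multiple: 19.9/8.62 = 2.309, or 2.31. The stated 2.19 does not reproduce.
5. Reciprocals: 1/2.19 = 0.457. Anything that rounds to 2.19 gives 1/2.195 = 0.456 to 1/2.185 = 0.458. A factor that rounds to 0.43 implies 1/0.435 = 2.30 to 1/0.425 = 2.35.
6. Rounding of 19.9, 431 and 98.0%: 19.85/(431.5 x 0.0205) = 2.24 to 19.95/(430.5 x 0.0195) = 2.38. The stated 2.19 lies outside.
7. Rounding of 1808 and 98.9% as well: unbound human AUC runs from 1807.5 x 0.0105 = 18.98 to 1808.5 x 0.0115 = 20.80, and the multiple from 2.15 to 2.48. To reach 2.19, unbound human AUC could be at most 2.195 x (431.5 x 0.0205) = 19.42, which contradicts the printed 19.9. Step 5 would still fail.
8. Other comparators: total exposure 1808/431 = 4.19; dog LOAEL, total, 1808/6418 = 0.28; rat NOAEL, unbound, 19.89/(63 x 0.020) = 15.8; dog NOAEL, total, 1808/518 = 3.49; rat kidney-toxicity AUC of 2030, 0.89 total or 0.49 unbound. None gives 2.19. The 19.8 target in Section 6.1.1 gives 19.8/8.62 = 2.30.
9. Size: 1 - 2.19/2.309 = 0.051, an understatement of about 5%.

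**The case against.** The Part 2 limits concern predicted exposure. Part 1 PK spans 0.1 to 105 mg, and Section 6.2 expects no accumulation. A prediction can therefore be made without the previous Part 2 cohort, and the 5.75 to 13 mg step lies inside Part 1 doses of 4.4 to 17.5 mg. That stands: a reader might infer that the limits cannot be checked at all without previous-cohort PK, and the documents do not support this. What remains is that Section 6.1 calls for previous-cohort data in addition to Part 1 data.

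A reader might also infer that the 2.26-fold dose step broke the cap. Nothing shows this. The values of Table 6.c are not in the available text, Section 6.2 reports the dose as safe and well tolerated, and Appendix F says that the Part 2 doses were set from available PK.

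There are other controls. AUC24 is calculated for every cohort, Section 11.0 gives any one reviewer a veto, and nothing in the conditional phrase permits a dose outside the limits. These reduce the risk, but none says that PK must be in hand at the review. The phrase may have been meant for PK beyond 24 hours; it does not say so.

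On the multiple, the objection is largely right. The absolute figures and the 0.43 are correct and already disclosed, the description in Section 6.1.1 of about twice the LOAEL exposure fits either value, and Part 2 is capped by Part 1 exposure, not by this number.

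**Conclusion.** The main point holds as an inconsistency in the escalation rules: one conditional phrase in the operative section against firm requirements in Sections 11.0 and 13.2 and the Part 2 dose-setting text. It bears on at most three cohorts, 24 subjects and 18 on TAK-020. Those are upper bounds that assume all seven Part 2 cohorts are run and that Cohorts 1 to 4 are the only ones dosed, as the amendment reports. It does not show that any cohort was escalated without PK. It is worth changing because it concerns dose setting in healthy volunteers and costs little.

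The 2.19-fold figure is a definite but minor error. It rests only on the protocol's printed inputs. A reader might infer that an exposure limit was derived from it and is therefore wrong; no limit in the protocol uses it.

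**What to change.** In Section 6.1.1, delete the condition on PK availability, or limit it to PK beyond the required minimum. Add one sentence: each Part 2 escalation requires review of the previous cohort's Day 9 PK from 0 to 24 hours. Naming Day 9 matters, because Day 1 also has a 24-hour profile, which would satisfy a general 24-hour rule while saying nothing about steady state.

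The Day 9 samples are already scheduled in Table 9.b, so no procedure is added. The cost is that a cohort waits if PK is late, which Sections 11.0 and 13.2 already imply. The 5-day interval in Section 6.1.1 has no stated starting point, so it should not be relied on to cover assay time after Day 9.

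In Section 6.2, replace 2.19-fold with 2.31-fold and keep 0.43. Leave the 19.8 target and its approximate description in Section 6.1.1 unchanged. This is one number in the next amendment.
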